**LIST OF ABBREVIATIONS**

AE	adverse event
CFR	Code of Federal Regulations
CRF	case report form
DMC	Data Monitoring Committee
DSMB	Data Safety Monitoring Board
FDA	Food and Drug Administration
GCP	Good Clinical Practice
HIPAA	Health Insurance Portability and Accountability Act of 1996
ICF	informed consent form
ICH	International Conference on Harmonisation
IEC	Independent Ethics Committee
IRB	Institutional Review Board
IV	intravenous
PI	Principal Investigator
SAE	serious adverse experience

## PROTOCOL SYNOPSIS

TITLE	The Role of Topical Antibiotic Prophylaxis in Eyelid Surgery
SPONSOR	UCSF
FUNDING ORGANIZATION	n/a
NUMBER OF SITES	1
RATIONALE	
As antibiotic resistance, antibiotic-related complications (e.g. contact dermatitis), and healthcare costs are on the rise, the routine use of post-operative topical antibiotic prophylaxis should be examined. After all, the rates of postoperative infections involving Class I and Class II surgical wounds (as defined by the CDC, or Centers for Disease Control and Prevention), including those associated with eyelid surgery, are known to be low.
 
Despite a lack of evidence supporting the use of prophylactic topical antibiotic therapy after eyelid surgery, the practice remains widespread both nationally and internationally. As such, we propose a randomized control trial testing the hypothesis that routine topical antibiotic prophylaxis does not significantly reduce the rate of infection after eyelid surgery.

STUDY DESIGN	This is a prospective randomized control trial.
PRIMARY OBJECTIVE	To determine if there is a role for topical prophylactic topical antibiotic therapy after eyelid surgery.
SECONDARY OBJECTIVES	To determine of rates of wound infection after eyelid surgery both with and without topical post-operative antibiotic prophylaxis; to determine if rates of wound infection after eyelid surgery are different among healthy and immunocompromised patients; to determine the type and frequency of adverse reactions resulting from topical antibiotic use.
NUMBER OF SUBJECTS	400
SUBJECT SELECTION CRITERIA	
Inclusion Criteria:
 
Patients aged 18 and older who are undergoing various eyelid procedures in an office, ambulatory care center, or operating room including but not limited to:
 
 
• blepharoplasty (upper and lower lids);
 
• ectropion repair;
 

	

• entropion repair;

• external dacryocystorhinostomy;

• external levator resection;

• eyelid lesion removal and/or biopsy;

• eyelid reconstruction and defect repair including after Mohs surgery;

• fat pad excision (upper and lower lids);

• gold or platinum weight implantation;

• internal levator resection;

• lateral tarsal strip;

• orbital fracture repair requiring periorbital incisions;

• orbitotomy requiring periorbital incisions;

• tarsorrhaphy;

• wedge excision.

• Patients undergoing repeat procedures will also be included.

 
Exclusion Criteria:
 

• Patients aged younger than 18 years old who are undergoing the above eyelid procedures in an office, ambulatory care centers, operating rooms;

• patients undergoing chalazion removal;

• patients who have had previous wound infections at the site of the procedure;

• patients with oral or IV antibiotic use within 10 days prior to procedure;

• patients requiring IV antibiotics during the procedure;

• patients with grossly contaminated or inflamed wounds;

• patients with human or animal bites,

• patients with wounds resulting from trauma

• patients allergic to all study drug options.

--	--

TEST PRODUCT, DOSE, AND ROUTE OF ADMINISTRATION	Topical Ophthalmic Antibiotic Ointment (e.g. poly-bacitracin, bacitracin). Apply a thin ribbon to surgical wounds 4 times a day (while awake) for 7 days.
CONTROL PRODUCT, DOSE AND ROUTE OF ADMINISTRATION	Artificial Tear Ointment (e.g. Refresh PM). Apply a thin ribbon to surgical wounds 4 times a day (while awake) for 7 days.
DURATION OF SUBJECT PARTICIPATION AND DURATION OF STUDY	Subjects will be on study for up to 14 days. Screening: During pre-operative assessment. Treatment Duration: 7 days Follow-up: 7-14 days The total duration of the study is expected to be 2 years with ongoing subject recruitment. Each subject will have a final follow-up at post-operative week 1 and/or post-operative week 2 unless a post-operative infection occurs. In the event of a post-operative infection, final follow-up will occur upon infection resolution.
CONCOMITANT MEDICATIONS	Allowed: All non-antimicrobial medications.  Prohibited: Antibiotics taken by IV or by mouth.
PRIMARY ENDPOINT	
 
To determine the rates of eyelid surgical site infections (SSIs) with and without topical antibiotic therapy.
 

SECONDARY ENDPOINTS	
 
To determine the rate of eyelid SSIs in patients with compromised immune status (e.g. patients with diabetes, those who smoke, those on chronic high-dose steroids, etc.)
 
To classify the types of complications related to antibiotic ointment and artificial tear ointment use; to determine their respective rates.
 

SAFETY EVALUATIONS	Adverse events will reported according to the UCSF IRB reporting requirements. Risks of participating in this study are not greater than the risks involved in current post-operative standard of care regimens.
PLANNED INTERIM ANALYSES	Serious adverse events will be monitored on an ongoing basis throughout the study. Study data from each subsequent set of 25 patients enrolled will be reviewed regularly by a Data Safety Monitoring Committee (DSMC).

STATISTICS Primary Analysis Plan	We will plan to use a T-test or a linear regression model (with no covariates other than study arm).
Rationale for Number of Subjects	We aim to recruit 200 people for each arm of the study, totaling 400 subjects. These numbers are commensurate to our regular surgical patient volume over the course of two years and as such, detected rates of infection will be clinically relevant.

## 1 BACKGROUND AND RATIONALE

Despite a lack of evidence supporting the use of routine topical antibiotic therapy (e.g. poly-bacitracin, bacitracin, erythromycin, etc.) after eyelid surgery, it is currently standard of care to provide patients with post-operative antibiotics in order to prevent surgical site infections (SSIs). For instance, a 2014 survey of oculoplastic surgeons from 43 countries revealed that while rates of prophylactic oral and perioperative intravenous antibiotic use varied considerably, topical antibiotic use was common across all geographic regions (85.2%).

The rates of postoperative infections involving Class I: Clean and Class II: Clean-Contaminated\* surgical wounds, including those associated with eyelid surgery, are known to be low. For instance, while the rate of infection after blepharoplasty is 0.2% with antibiotic ointment use and the rate of infection after external dacryocystorhinostomy is 1% with antibiotic use, the rates of infection without topical antibiotics in a range of dermatological procedures such as Mohs surgery are as low as 0.7%. There is currently no literature on the rates of infection after blepharoplasty and other eyelid-specific procedures in the absence of prophylactic antibiotic ointment.

As antibiotic resistance, antibiotic-related complications (e.g. contact dermatitis), and healthcare costs are on the rise, it has been advocated that topical antibiotic prophylaxis be withheld in eyelid surgery except in certain high risk cases. As such, we propose a randomized control trial testing the hypothesis that routine topical antibiotic prophylaxis does not significantly reduce the rate of infection after eyelid surgery. The hope is to reduce rates of antibiotic resistance, antibiotic-related complications, and healthcare costs.

\*Under CDC surgical wound classification system, Class I/Clean wounds include “an uninfected operative wound in which no inflammation is encountered and...[is] primarily closed and, if necessary, drained with closed drainage...Class II/Clean-Contaminated wounds include those ...without unusual contamination... [and] no evidence of infection or major break in technique.”

## 2 STUDY OBJECTIVES

### 2.1 Primary Objective

The objective is to conclusively determine whether or not topical post-operative antibiotic use has a meaningful prophylactic role after eyelid surgery.

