Title: The Role of Topical Antibiotic Prophylaxis in Oculofacial Plastic Surgery: A Randomized Controlled Pilot Study.

NCT number: NCT03199911

Document date: 4/1/2020

Statistical Analysis Plan (SAP)

The Role of Topical Antibiotic Prophylaxis in Oculofacial Plastic Surgery: A Randomized Controlled Pilot Study.

Principal Investigator

[name]

Professor of Ophthalmology

Department of Ophthalmology

University of California, San Francisco

San Francisco, CA 94143

Protocol identification number

IRB 17-22309

ClinicalTrials.gov identifier

NCT03199911

Author

[name] MD

Clinical Instructor and Fellow

Department of Ophthalmology

University of California, San Francisco

[figure not shown]
San Francisco, CA 94143

SIGNATURE PAGE

A handwritten signature in black ink, consisting of several overlapping loops and a long horizontal stroke extending to the right.

Principal Investigator

[name] (4/1/2020)

A handwritten signature in black ink, appearing to read '[name]' in a cursive style.

Author

[name] (4/1/2020)

Table of contents

| | |
|---|---|
| 1. Introduction..... | 5 |
| 2. Study design | 5 |
| 2.1 Sample size calculation..... | 5 |
| 3. Aims and objectives..... | 5 |
| 4. Outcomes | 6 |
| 4.1 Primary outcome | 6 |
| 4.2 Secondary outcomes | 6 |
| 4.3 Safety outcomes | 6 |
| 5. Populations and subgroups to be analyzed | 6 |
| 5.1 Populations..... | 6 |
| 5.2 Subgroups..... | 6 |
| 6. Analyses..... | 6 |
| 6.1 Primary outcome | 6 |
| 6.2 Secondary outcomes | 6 |
| 7. Missing data | 6 |
| 8. References..... | 7 |

1. Introduction

There is no consensus on the need for topical antibiotic prophylaxis after routine periocular surgery. This study is intended to act as a pilot to determine whether non-antibiotic ointment has a higher risk of infection than antibiotic ointment.

This statistical analysis plan (SAP) will give more detailed descriptions of the endpoints in the study and the corresponding analyses.

2. Study design

This is a randomized, unmasked clinical trial. Participants are recruited from the Oculofacial Plastic Surgery clinic at UCSF after deciding to proceed with periocular surgery. Inclusion and exclusion criteria are as detailed in the study protocol. The recruitment target is 400 individuals, approximately 200 per arm, based on the expected institutional surgical volume of eligible patients over a 2 year period.

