2.1 Sample size calculation

The primary outcome measure for the power calculation is the difference in surgical site infection frequency between the antibiotic and non-antibiotic arms.

| Sample Size per Arm | | Infection Rate (No Antibiotics) | | |
|-----------------------------------|------|---------------------------------|-------|-------|
| | | 0.7% | 2% | 4% |
| Infection Rate (With Antibiotics) | 0% | 1,388 | 483 | 239 |
| | 0.1% | 2,056 | 551 | 255 |
| | 0.2% | 3,200 | 633 | 273 |
| | 1% | 15,358 | 2,515 | 489 |
| | 2% | 1,386 | N/A | 1,239 |
| | | | | |

Based on these calculations, a non-inferiority study was deemed to be infeasible based on institutional surgical volume. Therefore, the decision was made to select a sample size approximating the surgical volume of eligible patients over a 2 year period in order to serve as a pilot study to detect whether a clinically relevant difference in infections occurred. For clean wounds, an infection rate greater than 5% is considered unacceptable(1-3); therefore, this sample size allowed 87% power at a 95% confidence level to detect a difference between an expected infection rate of 0.2% with antibiotics versus a maximum acceptable rate of 5% without antibiotics.

3. Aims and objectives

To study whether topical antibiotic prophylaxis significantly reduces the rate of infection after oculofacial plastic surgery.

4. Outcomes

This section will present the outcomes investigated to answer the study aims and objectives. The analyses are described in section 6 Analyses.

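### The protocol promises a conclusive answer on prophylaxis, but at its own cited infection rates 200 per arm cannot tell a benefit from no benefit

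*Protocol*

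**What the plan says.** **Protocol.** Section 2.1 gives the objective: "The objective is to conclusively determine whether or not topical post-operative antibiotic use has a meaningful prophylactic role after eyelid surgery". Section 1, like the synopsis, describes a trial "testing the hypothesis that routine topical antibiotic prophylaxis does not significantly reduce the rate of infection after eyelid surgery". The same section supplies the rates. With antibiotics, "the rate of infection after blepharoplasty is 0.2% with antibiotic ointment use" and "the rate of infection after external dacryocystorhinostomy is 1% with antibiotic use". Without them, "the rates of infection without topical antibiotics in a range of dermatological procedures such as Mohs surgery are as low as 0.7" per cent. It adds that no published rate exists for eyelid procedures without prophylactic ointment. The synopsis bases the 400 subjects on two years' surgical volume and gives no power, margin or equivalence criterion. Section 13.3 names a t-test or linear regression for the primary endpoint.

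**SAP (4/1/2020).** Section 1 says: "This study is intended to act as a pilot to determine whether non-antibiotic ointment has a higher risk of infection than antibiotic ointment". Section 2.1 tabulates sample sizes per arm (3,200 for 0.2% v 0.7%; 633 for 0.2% v 2%; 273 for 0.2% v 4%), calls a non-inferiority study infeasible, and claims 87% power for 0.2% v 5%, where 5% is a maximum acceptable rate and not an expected one. Section 3 gives the aim: "To study whether topical antibiotic prophylaxis significantly reduces the rate of infection after oculofacial plastic surgery". Section 6.1 specifies Fisher's exact test and a risk ratio with 95% confidence intervals. Neither document says how a non-significant result will be read.

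**The concern.** A trial that sets out to show that something does *not* significantly reduce infection is agreed with by every p>0.05, including those caused by too few events. That is tolerable only if the trial would probably reach significance when a worthwhile effect exists, or if a margin limits what can be claimed. Here there is no margin, and the rates in the protocol's background imply one or two infections per arm. If the objective and hypothesis stand, a null result could be taken as settling the question in a field where section 1 reports that topical antibiotics are standard of care. The SAP narrows the study to a pilot, so the two current documents also disagree on what the trial can deliver.

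**Working it through.** **Inputs.** 200 per arm (protocol 13.6; SAP 2). Rates from protocol section 1 and SAP 2.1. Fisher's exact test from SAP 6.1. The SAP does not state sidedness; two-sided 0.05 is assumed because it is what reproduces the SAP's figures. No loss to follow-up is assumed, which favours the trial.

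**Step 1: reproduce the SAP.** Power = Σ P(X=x)·P(Y=y) over all pairs (x, y) with Fisher p ≤ 0.05, where X ~ Bin(200, p₁) with antibiotics and Y ~ Bin(200, p₂) without.
- 0.2% v 5%: 87.1%, against the SAP's 87%. A one-sided test would give 92.8%, which does not match.
- The table is the two-sided 0.05, 80% power, continuity-corrected formula; all 14 numeric cells match. For 0.2% v 0.7% (δ = 0.005):
  - n = [1.96√(2·0.0045·0.9955) + 0.8416√(0.002·0.998 + 0.007·0.993)]² / 0.005² ≈ 2,812
  - corrected n = (2,812/4)·[1 + √(1 + 4/(2,812·0.005))]² ≈ 3,200.

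**Step 2: the protocol's cited rates, 0.2% v 0.7%.**
- Expected infections: 200 × 0.002 = 0.4 and 200 × 0.007 = 1.4. Relative reduction: (0.7 − 0.2)/0.7 = 71%.
- With 0 infections in the antibiotic arm, 5 in the other gives p = 0.061 and 6 gives p = 0.030, so at least 6 are needed. With 1, at least 8 are needed.
- P(X=0) = 0.998²⁰⁰ = 0.670 and P(Y≥6) = 0.00306, product 0.00205. P(X=1) = 0.269 and P(Y≥8) = 0.0001, product 0.00003. The sum is 0.0021, or about 0.2% power.
- No effect, 0.7% in both arms: chance of significance 0.16%.

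Non-significance is therefore 99.8% likely in both cases. Under the protocol's t-test the chance of significance at 0.2% v 0.7% is 3.6%, so non-significance is still 96.4% likely.

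**Step 3: larger rates without antibiotics (SAP scenarios, Fisher).**

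| With | Without | Power | Non-significant |
|---|---|---|---|
| 0.2% | 2% | 15.7% | 84.3% |
| 0.2% | 4% | 70.9% | 29.1% |
| 0.2% | 5% | 87.1% | 12.9% |
| 1% | 5% | 56.3% | 43.7% |

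Against 0.2%, 80% power is reached at about 4.5% (80.3%). The last row pairs the 1% that the protocol cites with antibiotics and the SAP's 5%.

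**Step 4: what a confidence interval could say.** The exact (Clopper–Pearson) upper 95% limit for the non-antibiotic arm with 0 of 200 infected is 1 − 0.025^(1/200) = 1.8%. For k infections it is the 0.975 quantile of Beta(k+1, 200−k): 4.3% for 3 and 5.04% for 4. With all 200 analysed, up to 3 infections would place that arm below 5%. At a true 0.7%, P(Y≤3) = 94.7%. So at the cited rate this reading would usually be informative where the p-value is not.

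**The case against.** The best defence is that the SAP already concedes the point. It prints the 3,200, drops non-inferiority, calls the study a pilot and claims power only against 5%. Its introduction asks whether infection is higher without antibiotics, and Fisher's test already has no difference as its null. A risk ratio with a confidence interval would normally expose the imprecision. All of this is true. It does not reach the protocol's objective or hypothesis: protocol section 13 lets the SAP modify the analysis plan, not objective 2.1, and SAP section 3 still poses a bare significance question. No threshold is given for reading the interval.

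The true rates may also be higher than those cited. The 0.7% is a low-end figure from dermatological procedures, the 0.2% is for blepharoplasty only, and the trial enrols a wider mix of operations, includes high-risk patients and accepts a single sign such as redness within its infection definition. This stands: the near-certainty in Step 2 is conditional on the cited rates.

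A reader might infer that non-significance is almost certain at every rate in the documents. It is not: power is 71% and 87% at the SAP's 4% and 5%. A reader might also infer that the investigators plan to declare that prophylaxis has no role, or to withdraw it. Neither document says so. Section 1 reports that withholding has been advocated and expresses a hope of less resistance, fewer complications and lower cost.

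**Conclusion.** The stated objective claims a property that the design lacks. At 0.2% v 0.7% the chance of a significant result is about 0.2% with Fisher's test, nearly the same as with no effect at all (0.16%), so a non-significant result there carries almost no information about benefit. The design can detect a large rise, to roughly 4.5% or more against 0.2%, and that is the question the SAP's pilot framing describes. The result assumes two-sided 0.05 and 200 analysed per arm. SAP section 7 excludes missing outcomes, so losses would generally lower power. The shortfall is in the objective, the hypothesis and the missing rule for interpretation; the SAP's power arithmetic is sound.

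**What to change.** 1. Protocol synopsis and 2.1: delete *conclusively* and restate the objective as the pilot question, namely whether non-antibiotic ointment produces a large increase in surgical site infection, towards the 5% that the SAP calls unacceptable. Reword the aim in SAP section 3 to match.
2. Protocol synopsis and section 1: make no difference the null hypothesis rather than the claim.
3. SAP 6.1: state that p>0.05 alone is not evidence that prophylaxis has no role. Add 95% confidence intervals for the risk difference and for the infection rate in the non-antibiotic arm, read them against the 5% level, and allow the statement that a large increase is excluded only if the upper limit lies below it. A rule that reads p>0.05 itself as no large increase would not do: at 1% v 5% the test misses the rise 44% of the time.
4. Record the change as an amendment dated relative to data collection, because SAP section 2 already describes randomisation and outcome assessment in the past tense.

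Cost: no added patients, visits or data. Protocol 15.1 requires IRB approval for the amendment, and the headline claim becomes less ambitious.

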### 2.2 Secondary Objectives

To determine of rates of wound infection after eyelid surgery both with and without topical post-operative antibiotic prophylaxis; to determine if rates of wound infection after eyelid surgery are different among healthy and immunocompromised patients; to determine the type and frequency of adverse reactions resulting from topical antibiotic use.

## 3 STUDY DESIGN

### 3.1 Study Overview

This is a single center, placebo-controlled, randomized trial. 400 subjects are planned. Subjects will be randomly assigned to a study drug or to a placebo. Each subject will apply a single dose of topical study drug or placebo four times daily to their surgical wounds over the course of one week.

Screening data will be reviewed to determine subject eligibility. Subjects who meet all inclusion criteria and none of the exclusion criteria will be entered into the study.

The following treatment regimens will be used:

- Experimental treatment: topical ophthalmic antibiotic ointment (e.g. erythromycin, bacitracin or polybac)
- Placebo: artificial tear ointment (e.g. Refresh PM)

Total duration of subject participation will be from the time of approval for eyelid surgery to post-operative visit #1 (either one or two weeks after surgery). Total duration of the study is expected to be 2 years.

## 4.2 Secondary Efficacy Endpoints

- The rate of superficial and deep SSI in high infection-risk groups such as patients with diabetes, those who smoke, those on chronic high-dose steroids, etc.
- The classification of types of complications (e.g. allergic dermatitis) related to antibiotic ointment and artificial tear ointment use as well as their respective rates.

## 4.3 Safety Evaluations

- Adverse events will be monitored throughout the study and will be reported according to the UCSF IRB reporting requirements.
- The DSMC will receive regular updates, including information such as: number of patients screened, number of participants enrolled, number of participants randomized/receiving treatment, number of participants lost to follow-up,

number of participants meeting the outcome definition, and number of participants with an adverse event. These updates will be made after each consecutive set of 25 participants has been enrolled.

- Stopping rule for the trial: As part of the regular DSMC review process detailed above, the DSMC will make a determination at each review whether the study can continue.

## **5 SUBJECT SELECTION**

### **5.1 Study Population**

Subjects requiring or electing to undergo eyelid surgery and meet the inclusion criteria will be eligible for participation in this study.

### **5.2 Inclusion Criteria**

Patients aged 18 and older who are undergoing various eyelid procedures in an office, ambulatory care center, or operating room including but not limited to:

- blepharoplasty (upper and lower lids);
- ectropion repair;
- entropion repair;
- external dacryocystorhinostomy;
- external levator resection;
- eyelid lesion removal and/or biopsy;
- eyelid reconstruction and defect repair including after Mohs surgery;
- fat pad excision (upper and lower lids);
- gold or platinum weight implantation;
- internal levator resection;
- lateral tarsal strip;
- orbital fracture repair requiring periorbital incisions;
- orbitotomy requiring periorbital incisions;
- tarsorrhaphy;
- wedge excision.
- Patients undergoing repeat procedures will also be included.
- Written informed consent (and assent when applicable) obtained from subject or subject's legal representative and ability for subject to comply with the requirements of the study.

